Acute hypoxemic respiratory failure (AHRF) is a common, life-threatening condition associated with substantial morbidity and mortality. Many acute and critical illnesses can cause AHRF, defined as a requirement for invasive or non-invasive ventilatory support with a PaO₂/FiO₂ ratio of 300 mm Hg or less. Patients with AHRF are vulnerable to lung and diaphragm injury associated with mechanical ventilation along with other nosocomial complications of critical care. While substantial progress has been made to reduce these risks and improve outcomes, many aspects of care for patients with AHRF remain untested and poorly defined. Novel approaches require careful evaluation in early phase studies to assess their potential to benefit patients before definitive evaluation in phase III trials. This platform trial will enable pilot/feasibility, phase II and phase III evaluation of a range of potential treatments to improve outcomes for patients with AHRF.

Objectives

The overarching objective of the PRACTICAL platform trial is to facilitate the development and evaluation of novel interventions for patients with AHRF. The primary endpoint for evaluation of these interventions will be specified for each domain, depending on its objectives and phase of investigation. This document is the Master SAP outlining the principles of randomization and analysis for this trial.

Section 2: Study Methods

Trial design

This study will use a randomised, embedded, multifactorial adaptive platform (REMAP) design [1]. This design is the basis of a perpetual trial to assess novel therapies for patients with AHRF efficiently and effectively. The trial is structured across independent *domains*, $d = A, B, C \dots$, where patients are allocated to two or more interventional arms, $j = 1, \dots, J_d$ (where J_d represents the total number of treatments in domain d). We will denote treatment j in domain d by d_j .

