This framework differs from standard (frequentist) analyses where conclusions are based on assessing the likelihood of the observed data under a null hypothesis. This standard framework typically requires the specification of a control treatment that will be considered optimal, unless the trial data give evidence to the contrary. As our Bayesian framework is based on considering the probability that each treatment is superior compared to all other competing strategies in the domain, we do not designate a control treatment in the analysis and consider all treatments as equal until the response data are available. Based on the response data, a continuously updated ranking of the treatment regimens can be computed based on their effectiveness compared to all competing treatment regimens to which participants are currently being randomised.

Statistical interim analyses and stopping guidance

In our perpetual trial, all statistical analyses will be considered interim analyses. We will aim to undertake analyses every three months using data from all individuals who have completed data collection for the domain-specific primary outcome. Note that interim analyses may be skipped if fewer than 50 participants have been enrolled in the platform since the last analysis. Interim analyses may also be delayed for operational reasons relating to data availability. At each interim analysis, we will analyse the data for all the domain/state combinations that are currently randomizing patients and are not in their pilot/feasibility phase. The goal of these analyses is to determine whether statistical conditions (outlined below) have been met to indicate that the current treatments for the domain/state combination should be changed. Formally, the statistical rules outlined below offer guidance; final decisions regarding stopping and publication will be made by the Platform Steering Committee (PSC) and the Domain Protocol Committee (DPC) as applicable, under advisement of the DSMB. Each domain/state combination will have a pre-specified

minimum recruitment level before these statistical triggers are computed, which we can consider as a “burn-in” period for the study.

Statistical Triggers

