The posterior distribution of the treatment effects will be estimated within each domain, separately for each state, using hierarchical models if appropriate (as defined by the domain specific protocol and SAP). For each state, we will compute the posterior probability that each treatment in the domain is superior, i.e., has the highest treatment effect among all treatments to which participants are currently being randomised. Treatments will be stopped in a specific domain and state combination, based on any of the following rules:

- 1) Stopped for superiority: randomisation will be stopped if one treatment has a high posterior probability of superiority, with the threshold specified in the domain specific protocol. All other treatments will be discontinued, and all study participants will receive this treatment until another treatment is considered for inclusion in the domain.
- 2) Stopped for inferiority: a specific treatment will be stopped for inferiority if the probability of superiority is small, as specified in the domain specific protocol. Note that a low posterior probability of superiority indicates a high posterior probability for harm.
- 3) Stopped for equivalence: if two treatments have a high posterior probability of being within the minimally important clinical difference (which we aim to harmonize across the domains with the same outcomes), then one of these treatments will be considered to stop for equivalence. If an equivalence trigger is met, the steering committee will determine which treatment is most suitable for stopping based on other data, e.g., safety.
- 4) Stopped for futility: futility can be declared in two manners: 1) Futility will be declared with respect to a given intervention, typically the standard or usual care and will be based on the probability that the treatment effect with respect to the standard intervention is less than a given threshold (e.g., a threshold larger than 1). Thus, this declaration of futility combines equivalence and inferiority. 2) The posterior probability of superiority is below a given threshold, where this threshold is larger than the inferiority threshold.

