The specific stopping rules for each domain and intervention will be specified in the domain specific protocol and SAP. All stopping decisions will be made separately for each intervention within each domain for each state. Thus, a domain will continue enrolling eligible patients until the statistical trigger has been met separately for all states. However, patients will only be randomised in a domain in states for which the statistical trigger has not been met. Note that once a statistical trigger has been met and randomisation has ceased to a specific treatment, it will no longer be included in the interim analyses. Thus, treatments cannot be “reinstated” in the trial once the statistical trigger has been met and confirmed by the DSMB.

Timing of final analysis

Once a statistical trigger has been met for a domain and state combination, and the stopping decision confirmed by the DSMB and (PSC) and/or (DPC), we will proceed with the final analysis. Note that the PSC and/or DPC can decide to defer the final analysis in some settings, i.e., an inferiority trigger is met in a 3-arm domain, where the final analysis would be deferred until superiority is reached for one of the remaining two treatments. The final analysis will take place when all individuals randomized in this domain/state combination before the statistical trigger was confirmed by the DSMB and the PSC and/or DPC have completed their follow-up for all primary and secondary outcomes. As hierarchical modelling may be used, individuals who are not

randomized to the specific domain/state combination may be included in the final analysis. Thus, the data used for the final analysis in a specific domain/state combination will be all participants who have completed follow-up when the final participant randomised to the focal specific domain/state completes their follow-up for the primary outcome. Follow-up is considered complete for the purposes of this final analysis at the time the primary endpoint, as specified in the domain-specific protocol, should have become available based on the date of randomization, even if the value for the outcome is missing. This final analysis dataset will be locked and considered final for the given domain/state combination, even if the results could change based on the dynamic borrowing and updated outcomes in other states.

Timing of outcome assessments

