Outcomes are collected in the iCORE, INDEX or I2 registries or in platform CRFs for sites not participating in a registry. Specific additional outcomes and their timing will be addressed in the domain specific protocols/SAPs.

Section 3: Statistical Principles

Statistical Reporting

All inferential statistics will be undertaken in a Bayesian framework [3]. Thus, when inferential statistics are used, we will report the posterior mean, median and 95% highest density credible interval for the parameter of interest. The primary analysis and pre-specified secondary analyses will also report the posterior probability of superiority (or its complement, inferiority). We will not report p-values and will not adjust for multiplicity as analyses are undertaken in a Bayesian framework [4]. Comprehensive simulations will be undertaken when a domain is added to ensure the proposed trial has good operating characteristics within each state.

Adherence and protocol deviations

Adherence and protocol deviations will be defined separately for each domain in the domain specific protocol and SAP. Adherence and protocol deviations will be presented using descriptive statistics by arm in each domain and state combination.

Analysis populations

Intention to Treat Population: All individuals who are randomised and meet the inclusion criteria and consent for the domain and state in which we are conducting the analysis. Individuals will be included in the intention to treat analysis irrespective of whether they received the treatment to which they were randomised. We may define some *delayed entry* domains, where individuals are only eligible for this domain after receiving other treatments, i.e., domains governing treatment in recovery. The intention to treat population for these domains will, similarly, include all individuals who meet the inclusion criteria and are consented for the domain. Thus, in delayed entry domains, the inclusion criteria will explicitly indicate the treatment and disease trajectory that must be followed to be eligible for delayed entry.

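### A low probability of being the best arm is read as harm and labelled inferiority, which is valid only in two-arm domains

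*SAP*

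**What the plan says.** Under Statistical Triggers (Section 2), a treatment is superior when it "has the highest treatment effect among all treatments to which participants are currently being randomised". The quantity computed is therefore P(best), a ranking against every current arm. Rule 2 uses it as follows: "a specific treatment will be stopped for inferiority if the probability of superiority is small, as specified in the domain specific protocol". The rule then interprets the trigger, without limiting the number of arms: "Note that a low posterior probability of superiority indicates a high posterior probability for harm".

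Section 3, Statistical Reporting, has the primary and pre-specified secondary analyses report the "posterior probability of superiority (or its complement, inferiority", so 1 − P(best) is given the name inferiority.

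Three other places bear on this:

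- Trial design (Section 2): "patients are allocated to two or more interventional arms".
- Framework (Section 2): "we do not designate a control treatment in the analysis".
- Timing of final analysis (Section 2) takes as its example the case where "an inferiority trigger is met in a 3-arm domain".

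A comparison with usual care appears among the triggers only in the first manner of declaring futility under rule 4. It does not appear in rule 2.

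**The concern.** Harm and inferiority are relative terms: an arm is harmful or inferior compared with something. With two arms the comparator is obvious, because an arm that is not best must be the worse of the two. With three or more arms, not being best means only that at least one other arm is better. It says nothing about where the arm stands against usual care, and rule 2 names no reference arm that would fill the gap.

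What is at stake is interpretation. The Framework section rests every trial conclusion on P(best). The data monitoring board and the committees that act on a trigger would be told that a small value signals harm, and a report could give a figure near 1 under the name inferiority for an arm that probably helps patients. A confirmed stop also cannot be undone, so the reason recorded for it matters.

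**Working it through.** The SAP states no effect size, sample size or threshold, so there is no planned figure to reproduce. The check is whether a low P(best) implies a high probability of harm.

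**Assumed inputs (none is in the SAP).** A binary favourable outcome; equal numbers n per arm; independent Beta(1,1) priors; observed rates equal to the assumed rates p. Each arm's posterior is then Beta(1 + np, 1 + n(1 − p)). P(best) and the pairwise probabilities come from 1,000,000 draws per arm.

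**Step 1: two arms.** With 68% against 60% and n = 300 per arm, the lower arm has P(best) = 0.021 and P(worse than the other arm) = 0.979. These sum to 1, so the SAP's sentence is correct here.

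**Step 2: three arms.** Results for the middle arm:

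| Usual care / middle / best | n per arm | P(best) | 1 − P(best) | P(better than usual care) | P(worse than usual care) |
|---|---|---|---|---|---|
| 60 / 68 / 78% | 200 | 0.012 | 0.988 | 0.952 | 0.048 |
| 60 / 68 / 78% | 300 | 0.003 | 0.997 | 0.979 | 0.021 |
| 60 / 68 / 78% | 400 | 0.0007 | 0.999 | 0.991 | 0.009 |
| 60 / 65 / 75% | 200 | 0.015 | 0.985 | 0.848 | 0.152 |
| 60 / 70 / 78% | 400 | 0.005 | 0.995 | 0.998 | 0.002 |

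The fourth column is what the SAP would call inferiority. The last column is harm relative to usual care. In these settings they lie at opposite ends of the scale.

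**Step 3: hand check of the n = 300 row by normal approximation.**

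- Middle against usual care: SD = √(0.68×0.32/300 + 0.60×0.40/300) = √0.001525 = 0.0391; z = 0.08/0.0391 = 2.05; probability about 0.98.
- Middle against best: SD = √(0.68×0.32/300 + 0.78×0.22/300) = √0.001297 = 0.0360; z = 0.10/0.0360 = 2.78; probability that the middle arm is the better of the two about 0.003.

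**Step 4: how often this would arise.** Single look, 4,000 simulated trials, true rates 60/68/78%, with assumed inferiority thresholds:

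| n per arm | Threshold on P(best) | Middle arm meets trigger | Meets it while P(better than usual care) > 0.95 |
|---|---|---|---|
| 200 | 0.01 | 47% | 17% |
| 200 | 0.05 | 73% | 30% |
| 400 | 0.01 | 80% | 58% |
| 400 | 0.05 | 94% | 69% |

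**Step 5: dependence on the number of arms.** With K identical arms, P(best) = 1/K, so 1 − P(best) = 1 − 1/K: 0.50 for two arms, 0.67 for three, 0.75 for four. The quantity labelled inferiority rises as arms are added, although no arm is worse than any other.

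**The case against.** The strongest reply is that the platform is a ranking design and says so: no control is designated, arms are ranked against one another, and conclusions rest on the probability of being best. Stopping an arm that beats usual care but loses to a better arm is then intended, and the SAP's three-arm example fits that reading. This stands. Nothing here shows that P(best) is the wrong trigger for dropping an arm.

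It is also fair that the triggers are advisory, that committees decide with the monitoring board's advice, and that each domain sets and simulates its own thresholds. These limit the practical damage. They do not repair the sentence, because no threshold turns P(best) into a measure of harm against usual care, and every domain inherits the master SAP's interpretation.

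A reader might go further and infer that beneficial arms will be published as harmful. The documents do not support that. Statistical Reporting also requires the posterior mean, median and credible interval, harms are handled separately and descriptively in Section 5, and the word harm is attached to this probability only in rule 2.

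A reader might also attack the second manner of declaring futility under rule 4 ("The posterior probability of superiority is below a given threshold, where this threshold is larger than the inferiority threshold"), since it uses the same probability with a looser cut and could end a two-arm domain on weak evidence. The Appendix leaves each domain to decide whether futility is used and for which treatments. An illustration with assumed superiority and futility thresholds of 0.99 and 0.05, eight looks and no true effect shows the dependence. Usual care is dropped in 15.9% of trials if futility applies to it, and in 3.9% if futility applies only to the experimental arm, the same as with no futility rule.

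**Conclusion.** The point holds as a fault of interpretation and labelling. The harm sentence in rule 2, and the use of inferiority for 1 − P(best) in Section 3, are valid for two arms and invalid in general for three or more. In the illustration with 300 per arm, the SAP's reading gives 0.997 where the probability of being worse than usual care is 0.021. The exact size depends on the assumed rates, sample sizes and thresholds, and the example needs usual care still being randomised together with a third, better arm. The logical gap depends on none of these.

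It does not follow that rule 2 must be rebuilt around a comparison with usual care, that dropping a dominated arm is a mistake, or that rule 4 is defective.

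**What to change.** 1. In rule 2, delete the harm sentence or limit it to domains with two arms.
2. For domains with three or more arms, base any statement of harm or inferiority on the pairwise posterior probability that the arm is worse than a named comparator, for example usual care.
3. In Section 3, Statistical Reporting, describe 1 − P(best) as the probability of not being the best current arm, and report the pairwise probability beside it.
4. Rule 2 may keep P(best) as its trigger, provided that it is labelled as a rule for dropping a dominated arm.

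The cost is a few sentences in the master SAP, with matching labels in the domain documents and reports. The pairwise probabilities come from the posterior already fitted. Because the trigger is unchanged, this wording does not call for new simulations; they would be needed only if a domain chose to alter the trigger itself.

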- The randomisation proportion for a given treatment cannot fall below $1 / (N + 2)$, where N is the number of treatments in the domain.
- The randomisation proportion for a given treatment cannot exceed $(N + 1) / (N + 2)$
- A new treatment added to the domain will be randomised at $1 / N$ for a burn-in period and all other treatments will be allocated using RAR in the remaining $(N - 1) / N$.

These randomisation proportions are set to maintain blinding to effect as clinicians administering the interventions cannot be blinded to the intervention.

Sample size

This study uses a perpetual design meaning that the sample size is not pre-defined. Domains will be stopped based on the stopping rules outlined in the stopping guidance section. Simulation methods will vary the number of individuals enrolled in the study to ensure good error control within each domain and to identify the number of patients that are likely to be required to draw sufficiently certain conclusions. Pilot/feasibility phases will have a fixed sample size, specified in the domain specific protocol.

Framework

Inferences in this trial will be based on a Bayesian statistical model, which estimates the posterior distribution of the parameter of interest, based on the accumulating data in the trial and pre-specified prior distributions. All trial conclusions will be based on the Bayesian posterior probability that a given treatment results in the best patient outcomes, measured by the domain-specific primary endpoint, compared to the current set of treatments randomized in that domain for individuals in that state. Study conclusions will be made separately for each state within each domain. However, where appropriate, we will use hierarchical modelling to dynamically integrate information across states to improve our ability to estimate the state-specific and domain-specific treatment effects. This borrowing can result in an increase in statistical power, while allowing for state specific treatment effects, and attenuate extreme results in smaller subgroups.

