3. The patient is moribund and deemed unlikely to survive past 24 hours (as determined by the clinical team)
4. The patient is being transitioned to a fully palliative philosophy of care

Each state/domain combination may have additional inclusion and exclusion criteria, which will be specific in domain protocols according to domain-specific requirements.

Platform Defined States

The platform structure defines multiple mutually exclusive patient states assessed at the time of randomization in a given domain. The pre-specified states for the platform include:

1. non-intubated patients;
2. intubated patients, not on extracorporeal life support, with low normalized respiratory system elastance (<2.5 cm H₂O/ml/kg predicted body weight);
3. intubated patients, not on extracorporeal life support, with high normalized respiratory system elastance (≥ 2.5 cm H₂O/ml/kg predicted body weight);
4. patients on extracorporeal life support.

Recruitment

We will use a CONSORT 2010 flow diagram to present the recruitment numbers within each domain/state combination. In addition to the screening data explained above, the CONSORT diagram will detail the number of patients who were lost to follow-up, discontinued the intervention were included/excluded from the primary analysis.

Withdrawal/follow-up

Patients can withdraw from the platform at any time and for any reason, upon request. The reason for voluntary withdrawal from the study will not be collected. Participants who choose to withdraw from the study can choose to either discontinue the study intervention but have their outcomes recorded or withdraw from all further data collection. Individuals who discontinue the study intervention but have their outcomes recorded will be included in the intention to treat analysis. All reasons for withdrawal will be tabulated and we will record whether the patient consented to further follow-up. The numbers (with reasons) of losses to follow-up over the course of the trial will be summarised by treatment arm for each domain and within each state.

Baseline patient characteristics

We will report the following baseline characteristics for all domains:

- 1) Age
- 2) Sex
- 3) Diagnostic reason for ICU admission
- 4) Respiratory support at randomization
- 5) APACHE
- 6) SOFA
- 7) P/F ratio
- 8) Ventilatory Ratio

We may also report domain specific baseline characteristic that will be specified in the domain specific protocol.

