Individuals can transition between disease states throughout the trial but will be included in the analysis for the state that they were in when they were randomised. All outcomes will be measured from the time of randomization into the domain. Additional pilot/feasibility outcomes for domain in this phase will be defined in the domain specific protocols, harmonized where possible. All additional outcomes will be defined in the domain specific protocols and SAPs.

Analysis methods

The specific outcome model will change depending on the outcome type. Thus, this section describes the general analysis approach. Statistical modelling will adjust for variation across sites, trial time period (in 2-week intervals), the stratification variables used in randomisation (if applicable), sex, age and potential domain specific variables. Adjustments will be made using a linear predictor framework, where the link function and error distribution will change depending on outcome type. The state-specific treatment effect for the randomised treatments within a domain will be estimated on the linear predictor scale and will be additive. When pre-specified in the domain specific SAPs, baseline effects and interaction effects between treatments in different domains will be estimated in the same model. Interaction effects will only be considered when treatments for the different domains are offered concurrently. The primary analysis will not consider treatment-covariate interactions, although pre-specified secondary analyses could consider these interactions and will be specified in the domain specific analysis plans. Hierarchical modelling will be used, where pre-specified, to borrow information about the treatment effect across states.

The specific treatment effect reported will change depending on the model used. We will endeavour to present treatment effects on an interpretable scale, i.e., hazard ratios rather than log hazard ratios. The mean treatment effect and 95% high density posterior credible interval will be calculated directly from the posterior distribution of the parameter from the regression. Thus, due to the flexibility of Bayesian modelling, we hope to report functions of the parameters estimated using the linear predictor framework and ensure interpretability of our findings.

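### The intention-to-treat definition adds an eligibility condition to randomisation, so it permits removal of patients judged ineligible afterwards; separately, a minor overlap leaves non-intubated ECLS patients without a unique state

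*SAP*

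**What the plan says.** **Analysis set.** SAP Section 3, Analysis populations, defines the intention-to-treat population as "All individuals who are randomised and meet the inclusion criteria and consent for the domain and state in which we are conducting the analysis". It then adds one protection: "Individuals will be included in the intention to treat analysis irrespective of whether they received the treatment to which they were randomised". For delayed-entry domains the same condition returns, and the set will "include all individuals who meet the inclusion criteria and are consented for the domain". Section 4, Withdrawal/follow-up, gives a second protection: patients who stop the intervention but allow outcome recording stay in. Neither protection concerns eligibility.

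**Blinding.** Section 2, Response Adaptive Randomisation, says that "clinicians administering the interventions cannot be blinded to the intervention".

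**States.** Section 4, Platform Defined States, says: "The platform structure defines multiple mutually exclusive patient states assessed at the time of randomization in a given domain". State 1 is "non-intubated patients", with no mention of ECLS. States 2 and 3 are intubated patients and expressly leave out those on ECLS. State 4 is "patients on extracorporeal life support", with no mention of intubation. Section 5, Outcome definitions, says that patients who change state "will be included in the analysis for the state that they were in when they were randomised".

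**The concern.** An intention-to-treat set protects the randomised comparison because membership is settled at allocation. Once membership also depends on meeting inclusion criteria, it can be revisited after the arm is known and the patient's course has been seen. Platform inclusion criterion 3 shows how: it asks whether hypoxaemia is mainly due to heart failure, fluid overload or pulmonary embolism. That is a judgement which later imaging or response to treatment can change. If such revisions are made or noticed more often in one arm, the groups compared are no longer those that randomisation formed.

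The wording also matters because every domain inherits it. The SAP's Appendix lists what domain documents must define under analysis populations: the per-protocol and safety sets. The intention-to-treat set is not on that list.

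The state overlap is a separate and smaller matter. State governs stratification in multi-state domains, the state-specific treatment effect and the separate stopping decisions, so each patient needs exactly one.

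**Working it through.** The plan gives no figure to reproduce. The check is one of text and logic, with one labelled illustration.

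**Step 1: does the eligibility clause do any work?** The definition joins three conditions: randomised, inclusion criteria met, consent given.
- Consent: Section 2, Randomization, has patients randomised once they are enrolled and consented, so this condition should remove few.
- Inclusion criteria: if every randomised patient were taken to meet them, the clause would be redundant. It changes the set only when it removes someone who was randomised.
- Protections: they cover non-receipt and discontinuation of treatment. No sentence retains a patient found ineligible, and no rule limits removal to blinded review of pre-randomisation data.

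Two analysts could therefore build different sets from this text. Section 2, Timing of final analysis, waits for everyone randomised in the domain/state combination, which is a wider group than Section 3 defines. The two are not reconciled.

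**Step 2: what could removal do?** Let both arms have true mortality m, and let a fraction f with mortality q be removed from one arm.

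Retained mortality = (m − f·q)/(1 − f)

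False difference = m − retained mortality = f·(q − m)/(1 − f)

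The SAP gives none of these inputs. Assume, for illustration only, m = 30%, f = 4% and q = 60%:
- Removal from one arm only: (0.300 − 0.04 × 0.60)/0.96 = 0.276/0.96 = 28.75%, a false difference of 30 − 28.75 = 1.25 percentage points.
- The same removal from both arms: 28.75% in each, false difference 0.
- Removal from one arm of patients at average risk (q = m): false difference 0.
- Removal from one arm of patients at lower than average risk (q < m): the sign reverses.

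The result runs from nothing to 1.25 points under the most one-sided of these assumptions, in either direction depending on which arm loses patients and what their risk is. It shows the mechanism and estimates nothing about this trial.

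**Step 3: are the states mutually exclusive?** Each combination of intubation, ECLS and elastance, matched to the four definitions:
- Non-intubated, no ECLS: state 1 only.
- Non-intubated, on ECLS: states 1 and 4.
- Intubated, no ECLS, elastance below 2.5: state 2 only.
- Intubated, no ECLS, elastance 2.5 or above: state 3 only.
- Intubated, on ECLS: state 4 only.

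There is one overlap. Such a patient can enter the platform, because the inclusion criteria in Section 4 list ECLS as one of several alternative forms of support and do not also require invasive ventilation. No precedence rule is given, and analysing by state at randomisation does not settle the matter when two states fit at that moment. Stopping is also decided by state, so if one of the two states has closed and the other has not, the SAP does not say whether this patient may still be randomised.

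**The case against.** The strongest reply on the analysis set is that the sentence merely says whose data belong to which domain and state in a multi-domain platform. The SAP describes no eligibility review after randomisation, and the timing section speaks of everyone randomised. A reader might infer from the wording that patients will be dropped; the SAP does not support that. What stands is that the text permits removal and says nothing to prevent it. The CONSORT diagram would show such exclusions but would not stop them.

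A reader might also think that re-measured elastance or a later change of state would remove or move a patient. It would not: Section 4 assesses state at randomisation and Section 5 analyses patients in that state. Only an error in the state first recorded stays open.

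Nor can it be said that most criteria are subjective. Among the platform inclusion criteria, age, type and duration of support, and oxygen level are factual; criterion 3 is the clear judgement. The more subjective platform items, such as anticipated extubation, are exclusion criteria, which the definition does not mention. Domain criteria are not shown.

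It would also go too far to say that this set underlies every stopping trigger. Section 2 bases interim analyses on patients with completed primary-outcome collection and does not name the intention-to-treat set.

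On the states, the intent is fairly clear. State 4 gathers ECLS patients, and the safety endpoints in Section 5 count a move to ECLS as an event for the non-intubated, which suggests that state 1 was meant to be ECLS-free. Where randomisation is stratified by state, one state must be chosen before allocation, so the choice cannot depend on arm. A reader might infer that such patients are excluded, or analysed in a wrong state, or that the arm comparison is biased. The text supports only that they have no unique state.

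**Conclusion.** The point on the analysis set holds: as written, the intention-to-treat definition allows patients to be removed after randomisation on eligibility grounds, in a platform whose treating clinicians are unblinded, and the wording carries into the domains. This rests on reading the eligibility clause as a real condition, which its place beside randomisation supports. Whether anyone would be removed, how many, and how unevenly between arms cannot be computed from the SAP. The point is worth correcting before analysis sets are built, but it is not evidence of bias.

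The overlap of states 1 and 4 is a minor internal inconsistency, limited to non-intubated patients on ECLS. Their number is not given and may be small. It affects stratification, state-specific analysis and stopping for those patients, and does not bias the comparison of arms.

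**What to change.** 1. In Section 3, define the intention-to-treat population as all patients randomised and consented in the domain, analysed by assigned arm and by the state recorded at randomisation, regardless of later eligibility findings. Use the same rule for delayed-entry domains, and say expressly that being randomised is required there too.
2. Move the restriction to patients who meet the criteria into a sensitivity set or the per-protocol set. Section 3 already makes per-protocol a subset of intention-to-treat but allows domains to have none; in those domains a sensitivity analysis is the place for it.
3. Separately, reconcile the state definitions in Section 4, for example by adding to state 1 the ECLS qualifier that states 2 and 3 carry or by stating which state takes precedence. Either gives each of the five profiles above exactly one state.

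The cost is a few sentences and one check that the randomisation tool records a single state. The statistical price is slight dilution of the effect from a few ineligible patients who stay in; the sensitivity analysis would show whether it matters.
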